#### **6.9.2.1. Serious Adverse Event Analyses**

The number and percentage of patients who experienced an SAE (including the SAEs that led to death) during the study drug period will be summarized by treatment using MedDRA PT nested within SOC. Events will be ordered by decreasing frequency within SOC.

#### **6.9.2.2. Other Significant Adverse Events**

The number and percentage of patients who permanently discontinued from study treatment due to an AE (including AEs that led to death) during the study drug period will be summarized by treatment using MedDRA PT nested within SOC. Events will be ordered by decreasing frequency within SOC.

Fisher's exact test will be performed to compare percentages for each LY3041658 dose group and Placebo at both the SOC and PT levels.

#### **6.9.3. Clinical Laboratory Evaluation**

Laboratory analyses will include planned analytes only. Planned analytes are those specified in the protocol. Summaries will be provided in both Système International (SI) and United States (US) conventional (CN) units (when different). Limits from the performing lab will be used to define low and high. Analyses of laboratory values will be produced using the measurements collected at scheduled time points. All unscheduled assessments will appear only in data listings.

- **Box plots for observed values:** Values at each visit (starting at randomization) will be displayed in box plots for patients who have both a baseline and a result for the specified visit. Unplanned measurements will be excluded. Original-scale data will be used for the display. These box plots will be used to evaluate trends over time and to assess a potential impact of outliers on central tendency summaries. The box plot will be a notched box for each treatment with outliers displayed, individual measurements outside

of reference limits will also be displayed using distinct symbols overlaying the box plot, and descriptive summary statistics will be included in a table below the box plot.

- Box plots for change values:** Change from baseline to each visit will be displayed in box plots for patients who have both a baseline and a result for the specified visit. Change from baseline to last observation will also be summarized and analyzed for patients who have both baseline and at least 1 postbaseline result. Baseline will be the last non-missing observation in the baseline period. The last non-missing observation in the Dosing Period will be used as the last observation. Unplanned measurements will be excluded. The box plot will be a notched box for each treatment with outliers displayed, change from baseline to last observation will be summarized within the box plot of changes (rightmost column), and descriptive summary statistics will be included in a table below the box plot, along with a p-value using the ANCOVA model containing terms for treatment and the continuous covariate of baseline measurement. Type III sums of squares will be used. The significance of within-treatment group changes from baseline will be evaluated by testing whether the treatment group LSMeans changes from baseline are different from zero using a t-statistic. In addition to the LSMeans and tests, the SD, minimum, Q1, median, Q3, and maximum will be displayed.

Alanine aminotransferase (ALT), aspartate aminotransferase (AST), and total bilirubin will not be included in this analysis as different ranges will be used as described in Section 6.9.5.

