7.1.1. Criteria for Permanent Discontinuation of Study Drug

Data collection and safety follow-up when study drug is permanently discontinued

If study drug is permanently discontinued, the participant will remain in the study to have an ETV, as well as post-treatment follow-up visits, as shown in the SoA (Section 1.3).

See the SoA for data to be collected at the time of discontinuation and follow-up and for any further evaluations that need to be completed. Safety follow-up is as outlined in the SoA (Section 1.3), Section 8.2 ("Safety Assessments), and Section 8.3 ("Adverse Events and Serious Adverse Events").

Criteria for permanent discontinuation of study drug

Possible reasons leading to permanent discontinuation of study drug include, but are not limited to, the following:

Participant decision

• The participant requests to discontinue the study drug.

Prohibited concomitant medication use

• The participant requires treatment with a prohibited medication (Section 6.5.4).

Pregnancy

• The participant becomes pregnant during the study (see Section 8.2.5.1).

Safety considerations

- The participant develops any of the following conditions during the study:
 - malignancy (except for successfully treated basal or squamous cell skin carcinoma)
 - HIV/acquired immune deficiency syndrome (AIDS) infection
 - active TB infection (Section 8.2.6)
 - HCV RNA positive (Section 8.2.8)
- The participant answered yes" to Question 4 or Question 5 on the "Suicidal Ideation" portion of the C-SSRS, or answered "yes" to any of the suicide-related behaviors on the Suicidal Behavior portion of the C-SSRS (Section 8.2.10).

Note: A psychiatrist or appropriately trained professional may assist in the decision to discontinue the participant.

- The investigator, after consultation with the sponsor's designated medical monitor, determines that a systemic hypersensitivity reaction has occurred and is related to study drug administration.
- The participant experiences any 1 of the following events on 2 consecutive samples taken at least 48 hours, but no more than 1 week, apart.
 - Total WBC <1000 cells/μL
 - Absolute neutrophil count (ANC) <500 cells/μL
 - Absolute lymphocyte count (ALC) <200 cells/μL
- The participant has an adverse event or serious adverse event or a clinically significant change in a laboratory value that, in the opinion of the investigator or sponsor, would preclude the participant from continuing to receive study drug.

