#### 6.9.4. Vital Signs and Other Physical Findings

Vital signs and physical characteristics include systolic blood pressure (SBP), diastolic blood pressure (DBP), pulse, weight, and BMI. Original-scale data will be analyzed. When these parameters are analyzed as continuous numerical variables, unplanned measurements will be excluded. When these parameters are analyzed as categorical outcomes and/or treatment-emergent abnormalities, planned and unplanned measurements will be included.

The planned analyses described for the laboratory analytes in Section 6.9.3 will be used to analyze the vital signs and physical characteristics, except for the inclusion of a threshold for change in addition to a limit for the definition of treatment-emergent. defines the low and high baseline values as well as the criteria used to define treatment-emergence based on post-baseline values.

**Table DSAD.6.1. Categorical Criteria for Abnormal Treatment-Emergent Blood Pressure and Pulse Measurement, and Categorical Criteria for Weight Changes for Adults**

Parameter	Low mmHg	High mmHg
Systolic BP (mm Hg) (Supine or sitting – forearm at heart level)	$\leq 90$ and decrease from baseline $\geq 20$	$\geq 140$ and increase from baseline $\geq 20$
Diastolic BP (mm Hg) (Supine or sitting – forearm at heart level)	$\leq 50$ and decrease from baseline $\geq 10$	$\geq 90$ and increase from baseline $\geq 10$

Pulse (bpm) (Supine or sitting)	<50 and decrease from baseline $\geq 15$	>100 and increase from baseline $\geq 15$
Weight (kg) (Consistent clothing and timing in relationship to meals and voiding)	(Loss) decrease $\geq 7\%$	(Gain) increase $\geq 7\%$

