#### **6.9.5.2. Renal Function Effects**

Effects on renal function will be assessed through analysis of elevated creatinine.

The CTCAE will be applied for laboratory tests related to renal effects (Table DSAD.6.2). This CTCAE grading scheme is consistent with both Version 3.0 and Version 4.03 of the CTCAE guidelines.

Shift tables will show the number and percentage of subjects from baseline to maximum during Period 1 and 2, with baseline depicted by highest grade during the baseline period. A shift table summary displaying the number and percentage of subjects with maximum postbaseline results will be presented by treatment group within the following categories:

- Decreased; postbaseline category < baseline category
- Increased; postbaseline category > baseline category
- Same; postbaseline category = baseline category.

Treatment-emergent lab abnormalities related to elevated creatinine occurring at any time during the Dosing Period will be tabulated using the CTCAE grades shown in Table DSAD.6.2. Planned and unplanned measurements will be included.

Treatment-emergence will be characterized using 5 criteria:

- any increase in postbaseline CTCAE grade from worst baseline grade
- increase to Grade 1 or above at worst postbaseline
- increase to Grade 2 or above at worst postbaseline
- increase to Grade 3 or above at worst postbaseline
- increase to Grade 4 at worst postbaseline.

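### SAP 6.9.3 keeps off-schedule hematology values out of the categorical laboratory summaries, in conflict with other sections of the SAP

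*SAP*

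**What the plan says.** SAP 6.9.3 states its inclusion rule in two sentences: "Analyses of laboratory values will be produced using the measurements collected at scheduled time points", and then "All unscheduled assessments will appear only in data listings". The rest of the section describes box plots of observed values, box plots of change from baseline, and an ANCOVA. It gives no method for treatment-emergent, shift or minimum/maximum tables.

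Other SAP sections expect such tables, or use a different inclusion rule:

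- 6.3.3 promises treatment-emergent high/low laboratory analyses.
- 6.9 refers to tables of categorical laboratory abnormalities and of shifts to the maximum value.
- 6.9.5.1 (hepatic tests) points back to 6.9.3 for changes to the minimum and maximum, and for treatment-emergent high or low results whenever they occur.
- 6.9.4 says of categorical vital signs that "planned and unplanned measurements will be included".
- 6.9.5.2 says of treatment-emergent creatinine abnormalities: "Planned and unplanned measurements will be included".

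Protocol 7.1.1 lists three cell-count criteria for permanent discontinuation, in cells/µL: "Total WBC <1000", "Absolute neutrophil count (ANC) <500" and "Absolute lymphocyte count (ALC) <200". Each must be met "on 2 consecutive samples taken at least 48 hours, but no more than 1 week, apart". Protocol 8.2.5 asks for clinically significant abnormal results to be repeated until they resolve or no longer matter clinically.

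**The concern.** LY3041658 neutralizes ligands that modulate neutrophil migration (Protocol 2.1). The protocol sets interruption and discontinuation rules on white cell, neutrophil and lymphocyte counts. Low counts are therefore a safety question that readers will want answered by arm.

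Off-schedule samples are likely to come from the participants with the most abnormal results, because those are the results the protocol asks sites to repeat. A scheduled-only rule for hematology can then leave a participant's lowest value out of the summaries. The SAP avoids this for creatinine and categorical vital signs but makes no such exception for hematology. A programmer who follows 6.9.3 literally and one who follows the reference in 6.9.5.1 would produce different tables.

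**Working it through.** The plan states no figure to reproduce. The check has three parts.

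**1. Can numbered visits supply both samples of a confirming pair?**

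Inputs: study days and tolerances from Protocol 1.3, Tables 1 to 3; the confirmation window of 2 to 7 days from Protocol 7.1.1. Visit 1 is left out because samples at Visits 1 and 2 both precede the first dose.

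Formula: shortest gap = (later study day − earlier study day) − tolerance of the earlier visit − tolerance of the later visit.

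| Consecutive visits | Study days | Calculation | Shortest gap |
|---|---|---|---|
| V2 to V3 | 1, 15 | 14 − 0 − 2 | 12 days |
| Each pair from V3 to V20 | 14 days apart | 14 − 2 − 2 | 10 days |
| V20 to V801 | 253, 281 | 28 − 2 − 7 | 19 days |
| V801 to V802 | 281, 323 | 42 − 7 − 7 | 28 days |

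The smallest gap is 10 days, and 10 > 7. No two numbered visits held within tolerance can form a qualifying pair. At least one of the two samples must be an unscheduled sample or come from an early termination visit, which has no fixed study day.

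**2. Which inclusion rule applies to which output?**

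| Output | SAP section | Unplanned values |
|---|---|---|
| Laboratory box plots, change from baseline, ANCOVA | 6.9.3 | Excluded |
| Hematology treatment-emergent high/low | 6.3.3; no method in 6.9.3 | Excluded if 6.9.3 governs |
| Treatment-emergent results without a timing limit | 6.9.5.1, referring to 6.9.3 | Implied in; 6.9.3 says out |
| Creatinine, treatment-emergent grades | 6.9.5.2 | Included |
| Categorical vital signs | 6.9.4 | Included |

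The scheduled-only rule suits the first row. Rows two and three are where the SAP is incomplete or contradicts itself.

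**3. What would one omitted participant mean?**

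One participant is 100/N percentage points of an arm. With the protocol's approximate arm sizes this is 100/42 = 2.4 points on LY3041658 and 100/21 = 4.8 on placebo. With the SAP's sizes it is 100/34 = 2.9 and 100/17 = 5.9. These figures give the scale of one omission. They do not predict how many will occur, because the documents give no expected rate of low counts or of off-schedule testing.

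**The case against.** The strongest reply is that little is hidden.

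- SAP 6.9 and 6.9.3 keep every value in listings, and with 51 to 63 participants listings are readable.
- The review of neutropenia and lymphopenia against infections (SAP 6.9.5.3) works from individual cases, so repeat values are available to it.
- Clinically significant laboratory changes are recorded as adverse events, and SAP 6.9.2 and 6.9.2.2 compare events, and discontinuations due to events, between arms.
- A first low value at a scheduled visit counts as treatment-emergent whether or not it is repeated.
- Scheduled-only tables also guard against unequal retesting between arms.

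All of this stands, and it limits the point. It rules out several stronger conclusions that a reader might draw:

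- *That no laboratory table uses unscheduled values.* The creatinine tables do.
- *That a repeat sample can never be tabulated, or that 0% of confirmed events can appear.* If the first low value is off schedule, the repeat can fall on a numbered visit 2 to 7 days later. It can also fall at an early termination visit, where hematology appears to be collected; the SAP does not say whether that visit counts as scheduled. In addition, the SAP plans no table of confirmed events, so 0% does not measure an effect of the inclusion rule.
- *That confirmed events vanish from the arm comparison or from the infection review.* The adverse event comparisons and the listings contradict this.
- *That the interruption criteria in Protocol 7.1.2.2 have the same problem.* They need no second sample; only an off-schedule low is affected.

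The reply does not resolve the conflict between sections. Adverse event tables depend on the investigator's judgment that a value is clinically significant, and they do not count laboratory values against limits. One could read the scheduled-only rule as covering only the box plots, but the sentence on unscheduled values carries no such restriction.

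**Conclusion.** The point holds as a conflict and a gap in SAP 6.9.3. Taken literally, the section leaves off-schedule hematology values out of the by-arm treatment-emergent and minimum/maximum summaries, against the reference in 6.9.5.1 and unlike the rules in 6.9.4 and 6.9.5.2. Numbered visits alone cannot show a confirmed pair under Protocol 7.1.1, because their shortest gap is 10 days against a window that closes at 7.

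This rests on two assumptions: visits are held within tolerance, and tolerance is counted from the planned study day. If it is counted from the previous visit instead, the shortest gap becomes 14 − 2 = 12 days and the result is the same.

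The number of participants affected cannot be estimated from the documents. The point concerns safety tabulation only; it does not touch the primary analysis and does not question any count threshold.

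**What to change.** In SAP 6.9.3:

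1. Include planned and unplanned measurements in categorical, treatment-emergent, shift and minimum/maximum analyses for all planned analytes, and describe those analyses there.
2. Keep scheduled values only for by-visit summaries, box plots and ANCOVA.
3. State how early termination values are handled.
4. Reconcile the section with 6.3.3, 6.9, 6.9.5.1 and 6.9.5.2.

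Optionally, add a by-arm count of participants with single and with confirmed values meeting the protocol's existing count criteria. This would be a new table and is not needed to correct the inclusion rule.

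The cost is SAP wording and some programming. The rule is already specified for creatinine and categorical vital signs, though the documents do not say that anything has been programmed. No protocol change or additional sampling is needed. Coverage depends on what reaches the database: Protocol 8.2.5 requires non-protocol local results in the CRF only when they change management or are judged clinically significant. The downside is small: participants retested more often have more chances to show an abnormal value, which a table footnote can state.

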9.4.5. Safety Analyses

Safety analyses will include adverse events, SAEs, AESIs, C-SSRS, vital signs, ECGs, and laboratory analytes, using the Safety Population data descriptively summarized by treatment group. Categorical safety measures will be summarized with incidence rates. Continuous safety measures will be summarized as mean change by visit. Exposure to study intervention will be calculated for each participant and summarized by treatment group.

Adverse events will be coded according to the *Medical Dictionary for Regulatory Activities* (MedDRA) and summarized by system organ class (SOC), preferred term, severity, and

relationship to the study intervention. A treatment-emergent adverse event (TEAE) is defined as an event that first occurred or worsened in severity after baseline, with baseline defined as all pre-existing conditions recorded at Visit 1 and any adverse events recorded before the first dose of study intervention (that is, during the interval between Visits 1 and 2 and recorded with the time of onset before the first dose of study intervention). The treatment periods will be used as the postbaseline period for the analysis. Safety analyses will be conducted separately for each treatment period. For events that are gender specific, the denominator and computation of the percentage will include only participants from the given gender.

The number and percentage of participants who experienced TEAEs, TEAEs by maximum severity, deaths, SAEs, TEAEs related to study intervention, discontinuations from the treatment due to an adverse event, and AESIs will be summarized. Treatment-emergent adverse events (all, by maximum severity), SAEs including deaths, and adverse events that lead to treatment discontinuation will be summarized and analyzed by MedDRA SOC and preferred term.

Treatment-related TEAEs (TEAEs related to study intervention) are defined as events that are indicated by the investigator on the eCRF to be related to treatment.

Adverse events of special interest will be identified by a standardized MedDRA query (SMQ) or a Lilly-defined MedDRA preferred term listing.

Suicide-related thoughts and behaviors occurring during treatment will be summarized based on responses to the C-SSRS consistent with the C-SSRS Scoring and Data Analysis Guide (Columbia Lighthouse Project WWW).

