#### **6.9.5.1. Abnormal Hepatic Tests**

Analyses for abnormal hepatic tests will involve 4 laboratory analytes: ALT, AST, total bilirubin, and ALP. In addition to the analyses described in Section 6.9.3, this section describes specific analyses for this topic.

The central laboratory reference ranges (CLRM reference ranges) will be used for these laboratory assessments (ALT, AST, total bilirubin, and ALP).

Analyses for change from baseline to last observation, change from the baseline value to the minimum value during Period 1 and 2, change from the baseline value to the maximum value during Period 1 and 2, and treatment-emergent high or low laboratory results at any time are described in Section 6.9.3.

The patients with the following abnormal elevations in hepatic laboratory tests at any time will be listed for both Period 1 and 2:

- ALT measurement  $\geq 3$  times,  $\geq 5$  times and  $\geq 10$  times the central laboratory ULN.
- AST measurement  $\geq 3$  times,  $\geq 5$  times and  $\geq 10$  times the central laboratory ULN.
- Total bilirubin measurement  $\geq 2$  times the central laboratory ULN.
- ALT or AST measurement  $\geq 3$  times the central laboratory ULN and total bilirubin measurement  $\geq 2$  times the central laboratory ULN
- ALP measurement  $\geq 2$  times the central laboratory ULN.

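### SAP 6.9.3 drops ALT, AST and total bilirubin from its laboratory outputs and 6.9.5.1 refers them back to 6.9.3, so neither section gives a working by-arm summary, contrary to SAP 6.3.3 and Protocol 9.4.5

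*SAP*

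**What the plan says.** **SAP 6.9.3 (Clinical Laboratory Evaluation)** uses the performing laboratory's limits to define low and high. It describes two outputs: box plots of observed values by visit, with symbols marking measurements outside the reference limits, and box plots of change from baseline by visit and to last observation, with an ANCOVA on treatment and baseline. It closes by excluding three analytes: ALT, AST and "total bilirubin will not be included in this analysis as different ranges will be used as described in Section 6.9.5".

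**SAP 6.9.5.1 (Abnormal Hepatic Tests)** has a wider scope: "Analyses for abnormal hepatic tests will involve 4 laboratory analytes: ALT, AST, total bilirubin, and ALP". It presents itself as a supplement: "In addition to the analyses described in Section 6.9.3, this section describes specific analyses for this topic". It sets a different reference: "The central laboratory reference ranges (CLRM reference ranges) will be used for these laboratory assessments (ALT, AST, total bilirubin, and ALP". It then says that change to last observation, change to minimum, change to maximum, and "treatment-emergent high or low laboratory results at any time are described in Section 6.9.3". For the ULN multiples it specifies one output: "The patients with the following abnormal elevations in hepatic laboratory tests at any time will be listed for both Period 1 and 2".

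**SAP 6.3.3 (Analysis Methods)** calls for an ANCOVA of continuous laboratory variables with treatment and baseline in the model, treatment-emergent high/low outputs, and Fisher's exact test for categorical safety data. It exempts no analyte.

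**Protocol 9.4.5 (Safety Analyses)** has laboratory analytes summarized by treatment group and states: "Categorical safety measures will be summarized with incidence rates. Continuous safety measures will be summarized as mean change by visit". It does not exempt the liver tests either.

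**The concern.** Each section hands the three analytes to the other. A programmer who follows the specific text would leave ALT, AST and total bilirubin out of the laboratory figures and the ANCOVA, look in 6.9.3 for the minimum, maximum and high/low methods, find none, and produce only a listing.

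These tests carry weight in this trial. The criteria in Protocol 7.1.1 for considering discontinuation on liver grounds are built on ALT, AST, ALP and total bilirubin. Protocol 2.3 reports a Grade 3 GGT elevation in the multiple-dose Phase 1 study, without ALT or AST above 3 times ULN. Because randomization is 2:1, a patient listing is also a poor basis for comparing arms unless denominators are attached.

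**Working it through.** The plan states no figure on this point, so the check follows each liver output through the two sections.

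1. **Observed values by visit.** Described in 6.9.3; ALT, AST and total bilirubin are excluded there. Section 6.9.5.1 does not mention this output separately. Result: no operative specification.
2. **Change from baseline by visit and to last observation, with ANCOVA.** Described in 6.9.3; the three analytes are excluded. Section 6.9.5.1 sends change to last observation back to 6.9.3. Result: a closed loop.
3. **Change to minimum and to maximum.** Section 6.9.5.1 cites 6.9.3. Section 6.9.3 describes neither, for any analyte. Result: cited but not written.
4. **Treatment-emergent high or low.** Section 6.9.5.1 cites 6.9.3. Section 6.9.3 says which limits define low and high but gives no treatment-emergent analysis. SAP 6.3.3 says the output will be produced but gives no definition or choice of range. SAP 6.9.4 (vital signs) also relies on a treatment-emergent definition in 6.9.3 that is not there. Result: cited by two sections and defined in neither 6.9.3 nor 6.3.3.
5. **ULN multiples** (ALT and AST at 3, 5 and 10 times; total bilirubin at 2 times; ALT or AST at 3 times with total bilirubin at 2 times; ALP at 2 times). Listing only. Result: no count or percentage by arm.

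**Does the stated reason support the exclusion?** The two sections do use different ranges: performing-laboratory limits in 6.9.3 and central ranges in 6.9.5.1. Within the outputs that 6.9.3 describes, limits enter in one place, the overlay symbols on the observed-value plots. Change from baseline and the ANCOVA use no limits. The reason would fit a high/low analysis, but 6.9.3 contains none.

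**Is the exclusion consistent with its own reason?** No. Section 6.9.5.1 gives ALP central ranges as well, yet 6.9.3 does not exclude ALP. ALP is therefore read against performing-laboratory limits in one section and central ranges in the other.

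**Comparison within the SAP.** For creatinine, 6.9.5.2 specifies shift tables with number and percentage by treatment group and tabulates treatment-emergent CTCAE grades. The hepatic section has no equivalent.

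**Why denominators matter (assumed counts).** Protocol 9.2 plans about 42 participants on LY3041658 and 21 on placebo. If 3 patients in each arm were listed at a given threshold, the listing would show equal counts, while the rates would be 3/42 = 7.1% and 3/21 = 14.3%. The counts are invented and serve only to show what a listing leaves out.

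**The case against.** The strongest reply is that the general rules already cover these analytes. SAP 6.3.3 requires ANCOVA for laboratory variables with differences from placebo and confidence intervals, treatment-emergent high/low output, and Fisher's exact test for categorical safety data. Protocol 9.4.5 requires by-arm summaries. Section 6.9.5.1 itself opens on the footing that the 6.9.3 analyses apply to all four hepatic analytes.

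This stands against two stronger readings that a reader might infer. The first is that the plan never summarizes ALT, AST or total bilirubin by arm. The documents contradict themselves on this; they do not adopt that omission. The second is that a liver signal could not be judged against placebo. ALP, GGT and direct bilirubin are in the chemistry panel and are not excluded, adverse events are compared by arm at system organ class and preferred term level, and an internal committee reviews unblinded safety data. The Phase 1 Grade 3 event was in GGT, which keeps the full 6.9.3 output, and the discontinuation criteria apply to individual participants without depending on SAP tables. It is also fair that reference limits do play a part in the observed-value plots, and that in a trial of about 63 participants the threshold cases could be tallied by hand from the listing.

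The reply does not remove the defect. A named exclusion in a specific section would ordinarily be taken to override a general rule. SAP 6.3.3 does not say which range defines high or low, and 6.9.3 and 6.9.5.1 differ on that. Neither general rule specifies tables for the ULN multiples. If the general rules do govern, the exclusion sentence is wrong as it stands, so a correction is needed on either reading.

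**Conclusion.** The point holds as an internal contradiction with two unwritten methods. For ALT, AST and total bilirubin, 6.9.3 and 6.9.5.1 read literally give no operative by-arm summary, and this conflicts with SAP 6.3.3, Protocol 9.4.5 and the opening of 6.9.5.1. The minimum/maximum and treatment-emergent high/low analyses credited to 6.9.3 are not described there. The ULN thresholds are specified as a listing only. The stated reason does not justify dropping change from baseline.

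The extent is three analytes, plus an inconsistency for ALP. No sample size, power or efficacy result is affected. The conclusion rests on taking the exclusion to cover both outputs described immediately before it; its wording leaves that scope open, which is itself part of what needs correcting. The sponsor should correct this, but it is not evidence that liver safety was meant to go unsummarized.

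**What to change.** 1. In SAP 6.9.3, limit the exclusion to high/low flagging against performing-laboratory limits. Keep ALT, AST and total bilirubin in the observed-value plots and in the change-from-baseline plots and ANCOVA, using central ranges for the overlay symbols. Deleting the sentence outright would place these analytes under performing-laboratory limits, against 6.9.5.1.
2. In 6.9.5.1, write out the change to minimum, change to maximum and treatment-emergent high/low analyses with central ranges, in place of the reference to 6.9.3.
3. For the thresholds already printed in 6.9.5.1, report n (%) by treatment group and period, with the listing as support.
4. Treat ALP the same way in both sections.

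The cost is SAP wording and one or two extra tables. Data collection and trial conduct do not change.
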